8.6. Data Management

Data collection and data source is described in Section 8.4.

- All participant data relating to the study will be recorded on eCRFs unless transmitted to the sponsor or designee electronically (e.g., laboratory data). The investigator is responsible for verifying that data entries are accurate and correct by physically or electronically signing the CRF. Guidance on completion of eCRFs will be provided in eCRF completion guidelines.
- The sponsor or designee is responsible for the data management of this study including quality checking of the data. Detailed information about study data collection and management process including systems used can be found in the study Data Management Plan (DMP) or equivalent contract research organisation (CRO) document.
- The sponsor assumes accountability for actions delegated to other individuals (e.g., contract research organisations [CROs]).

More granular level process for data management will be described in the overarching study DMP.

8.6.1. Timings of Assessment during Follow-up

Patients will be followed for 28 days from the time they received sotrovimab treatment (index date (D0)) in one of the clinical sites. Data and samples will be collected following the schedule below (see also Table 1):

- Day 0 On-site screening:
 - Confirmation that decision to administer sotrovimab (per standard of clinical care) has been made by the treating HCP
 - Informed consent and enrolment
 - Baseline sample collection under supervision after training (nasal/oropharyngeal) prior to sotrovimab administration or if not possible, then either during sotrovimab infusion or as close as possible to the end of sotrovimab infusion (within ≤ 2 hours of the end of the sotrovimab infusion).

- Data collection of patient and disease characteristics (e.g. demographic, medications and comorbidities) when possible
- Three sample collection kits must be provided to the patient for home collection at each follow up timepoints (D7, D14, D28 [+/-2days]), with subject identification present on each kit (as per guidance in the study reference manual).
 - Day 7 +/- 2 days
 - Phone call: Data collection of clinical outcomes and any treatment related AEs reported by the patient, concomitant medications if any changes
 - Follow-up sample collection (nasal/oropharyngeal) – Home kit
 - Retrospective collection of baseline data with the patient or directly with patient HCP when not possible at Day 0
 - Day 14 +/- 2 days
 - Phone call: Data collection of clinical outcomes and any treatment related AEs reported by the patient, concomitant medications if any changes
 - Follow-up sample collection (nasal/oropharyngeal) – Home kit
 - Retrospective collection of baseline data with the patient or directly with patient HCP when not possible at Day 0
 - Day 28 +/- 2 days
 - Phone call: Data collection of clinical outcomes and any treatment related AEs reported by the patient, concomitant medications if any changes
 - Follow-up sample collection (nasal/oropharyngeal) – Home kit
 - Retrospective collection of baseline data with the patient or directly with patient HCP when not possible at Day 0

For patients progressing to severe COVID-19 and being hospitalised – see Section 8.1.

The follow-up of patients with a persistent positive sample at the end of the study period (i.e. Day 28) is described in Section 8.7.2 as an exploratory analysis. Persistent positive results will be reported back to the sites upon site request (as described in the study reference manual).

8.7. Data analysis

8.7.1. Essential Analysis

This study is descriptive. Categorical variables will be described using counts, proportions and 95% CI and continuous variables will be described using measures of central tendency (e.g. mean, interquartile range, etc.)

8.7.1.1. Primary Objective

- Sequencing of samples on a regular basis (as detailed in the study laboratory manual) is required.
- The primary analysis of data will include:
 - Proportion of patients eligible for sequence analysis that have any AA change from baseline in the epitope of sotrovimab binding

- Proportion of patients eligible for sequence analysis that have any AA change from baseline in the spike protein
- More details on any sub-analyses performed by sub-groups will be described in the SAP.

8.7.1.2. Secondary Objective

- VOC, VUI and other lineages information as classified by UKHSA and WHO will be identified from sequencing data for patients eligible for sequencing analysis (Secondary Objective 1)
 - This analysis will be done on the earliest possible sample and reported only once per patient as described in the SAP
- Comorbidities, clinical outcomes, patients with undetectable SARS-VoV-2 viral ribonucleic acid and safety events data will be described and reported with counts and proportions with a 95% CI (Secondary Objective 2 and 3).
- AA (detected at >5% allelic frequency) changes in the SARS-CoV-2 spike protein in samples collected at Day 7, 14 and 28 (+/-2 days) compared to baseline following sotrovimab administration for samples with viral loads above the threshold of the sequencing assay (Secondary Objective 4)
- AA changes in the SARS-CoV-2 spike consensus sequences from baseline in samples where viral load is insufficient for >5% allelic frequency analysis but sufficient to generate consensus level sequencing data (Secondary Objective 5)

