Collected nasal mid-turbinate swabs have demonstrated comparable sensitivity and good viral load correlation to clinician collected nasopharyngeal swabs (considered as the gold standard) for COVID-19 detection [Kojima, 2021; Alemany, 2021]. While the nasal/oropharyngeal sample will be collected on site at baseline under supervision after training (as detailed in the study reference manual), home test kits will be provided to the patients with clear explanations on the appropriate technique to collect the follow-up samples as well as instructions for return to the central analytical laboratory. The patient's subject identification number must be present on each of the home test kits (follow guidance in the study reference manual) and checked by study research staff, when these are provided to the patient to take home. Collection of the follow-up samples may also be performed by an HCP in case of hospitalisation. Home test kits are proposed to minimise patients' exposure to healthcare settings that in-person visits would require and to improve patient adherence to study-related procedures and follow up. All the samples will be sent to a central analytical laboratory for testing (i.e., viral load, and sequencing analyses amongst SARS-CoV-2 positive samples with sufficient viral load) (see Section 8.3.2).

Select key clinical outcomes data (e.g. hospital admission, respiratory support, ICU admission and death) will be collected at Day 7, 14 and 28 (+/-2 days) and documented in the eCRF. Phone calls to the patients by the study research staff will be planned at these three follow-up time points with the aim to complete the eCRF and to remind the patients to collect their follow-up nasal/oropharyngeal sample.

Table 1 Schedule of Activities

| | Baseline (Day 0, sotrovimab index date) | Follow Up Call 1 (Day 7 ± 2)^p | Follow Up Call 2 (Day 14 ± 2)^p | Follow Up Call 3 (Day 28 ± 2)^{pq} |
|---|--|---|--|---|
| Pre-screening ^a | √ | | | |
| Confirmation of sotrovimab prescription ^b | √ | | | |
| Informed Consent ^c | √ | | | |
| Eligibility confirmation ^d | √ | | | |
| Enrolment ^e | √ | | | |
| Nasal nasal/oropharyngeal swab | √ ^f | √ ^g | √ ^g | √ ^g |
| Sotrovimab administration ^h | √ | | | |
| Demography ⁱ | √ | | | |
| Co-morbidities ^j | √ | | | |
| Disease characterisation ^k | √ | | | |
| Concomitant medications ^l | √ | √ | √ | √ |
| Vaccination status ^m | √ | √ | √ | √ |
| Clinical Outcomes ⁿ | | √ | √ | √ |

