SARS-CoV-2 Genomic analysis will be performed by the assigned central analytical laboratory, University College of London (UCL), receiving all study patients nasal/oropharyngeal swab samples as described in the Study Lab Manual. [Figure 2](#) shows genomic and viral load data movement between UCL, Syneos Health, and GSK. UCL generates the raw sequencing FASTA/FASTQ and related files which would then be uploaded to UK HSA/CLIMB database by UCL as part of MHRA requirements in-stream. UCL also takes the responsibility to upload the raw sequencing files to GSK via sFTP in near real-time which GSK will be using for bioinformatic analysis of amino acid substitutions in spike protein. UCL uses its bioinformatic pipeline to create a Pharmacology File (PF) having only viral variant calling VOC/VUI information based on the whole genome sequence and sends it to Syneos Health for analysis and MHRA reporting.

GlaxoSmithKline (GSK)

GSK receives the raw sequencing files from UCL and create its own bioinformatic pipeline to create another Pharmacology File consisting of amino acid substitutions in spike protein and sends it to Syneos Health for statistical analysis and MHRA reporting. The interim and final reports would be shared with MHRA directly by GSK.

This document is confidential.

Syneos Health (SYNH)

Syneos Health receives Pharmacology Files (PF) from both UCL and GSK and will perform study management, clinical data management and statistical analysis for MHRA interim and final analysis.

UCL will share PF (VOC/VUI based on the whole genome sequence) and viral load data in excel (.csv) format using dedicated SFTP according to agreed Data Import Agreement (DIA) with SYNH. Likewise, GSK will share the bioinformatic analysis of amino acid substitutions in spike protein file under excel (.csv) format using dedicated SFTP according to agreed Data Import Agreement (DIA) with SYNH. The data transfer from GSK and UCL to SYNH would be in cumulative fashion, and all reporting would also be cumulative each time. The data will be stored at SYNH server (M: Drive).

SYNH would merge the sequencing data (PF) coming from GSK with UCL (VOC/VUI based on the whole genome sequence and "AA Change from Baseline" will be derived for analyses (i.e., Interim and Final).

Viral load data will be received from UCL and SYNH takes responsibility for conversion of copies/mL into log10 copies/mL for analysis.

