8.2 Key Definitions

End of Study (EOS)

The EOS is defined as the date the last participant completes the last visit as shown in the Schedule of Activities in [Section 4.8](#).

Study day

Event date can be adverse events, labs, or any other assessments during the study.

If the event date \geq date of first dose of sotrovimab, study day = event date – date of first dose of sotrovimab + 1.

If the event date $<$ date of first dose of sotrovimab, study day = event date – date of first dose of sotrovimab.

Baseline Value

Baseline value will be defined as the last non-missing value recorded prior to sotrovimab administration or as close as possible to the end of sotrovimab infusion.

Retrospective collection of baseline data with the patient or directly with patient HCP will be conducted when not possible at Day 0. In all cases baseline is defined to be Day 0.

Change from Baseline (CFB)

CFB = Post-baseline value – Value at baseline

Treatment Emergent

Treatment emergent amino acid substitutions include subjects where baseline and post-baseline records exist.

Treatment emergence for consensus will include baseline records of allelic frequency $>5\%$ and post-baseline $>50\%$ as thresholds, whereas treatment emergence for minority will include baseline records of allelic frequency $>5\%$ and post-baseline $>5\%$ as thresholds.

Consensus sequence is defined as allelic frequency $>50\%$ and minority species with allelic frequency $>5\%$.

Lower Limit of Detection (LLOD)

LLOD of the assay is defined as 453 copies/mL (equivalent to Ct=38).

Lower Limit of Quantification (LLOQ)

LLOQ of the assay is defined as 1570 copies/mL (equivalent to Ct=36.18).

Viral load Negatives

The threshold to declare a viral load negative is the LLOD.

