9.5 Prior and Concomitant Medication

Prior and concomitant medications will be coded by the Anatomical Therapeutic Chemical (ATC) classification system according to the World Health Organization Drug Dictionary (WHO-DD). Medications will be classified as concomitant or prior and summarized by ATC class (level 2, therapeutic subgroup) and preferred drug name for all subjects in the safety population.

Prior medication is defined as any medication taken before the date of the first dose of study treatment. Concomitant medication is defined as any medication taken on or after the date of the first dose of study treatment.

Concomitant medication will be recorded, including the medication name, daily dose, unit, regimen, administration route, reason for administration (text field) and medication start and end dates or ongoing. All prior and concomitant medications will be listed, with a flag identifying prior medications, for all subjects in the Safety population.

The summary tables will show the frequency and percentage of subjects in each group with at least one usage of medication on the sub-class level within each ATC class sorted alphabetically.

10. Efficacy

Treatment Emergent Amino acid Substitutions/Amino acid Change from Baseline is defined as any amino acid substitutions detected at post-baseline visits compared to baseline sequence.

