10.2 Secondary Efficacy Endpoint and Analysis

Secondary efficacy analyses will be conducted for the safety populations, unless otherwise stated.

The secondary endpoints in this study are:

- Proportion of patients eligible for sequence analysis with SARS CoV-2 VOC/VUI on the earliest possible sample.

The proportion of patients with VOC/VUI will be summarized showing the counts and percentages of patients by each variants based on WHO classification and Pango sub-lineage for the earliest possible VOC/VUI sample including baseline. A data listing including WHO label and Pango sub-lineage will be provided.

- Proportion of patients with undetectable virus (i.e. viral load < LLOD)

Summary of proportion of patients with undetectable virus would be based on safety population and summarized by Day 7, 14 and 28 (+/-2 days).

- Clinical outcomes through Day 28 post-sotrovimab treatment:

The following clinical outcomes will be summarized by count and percentage of patients and its 95% CI by VOC/VUI, Non-VOC/VUI, and Overall:

- Proportion of patient with all-cause hospital admissions
- Proportion of patient with COVID-19 related hospital admissions.
- Proportion of patients requiring new or increased oxygen support (supplemental oxygen [not high flow], non-invasive ventilation or high-flow, invasive mechanical ventilation, or Extracorporeal membrane oxygenation [ECMO])
- Proportion of patient with all-cause ICU admissions.
- Proportion of patient with COVID-19 related ICU admissions.
- Proportion of patient who died through Day 28.
- Proportion of patient who died through Day 28 due to COVID-19.

In addition, the clinical outcomes would also be summarized by VOC/VUI variants and also by Medical Condition/Comorbidity.

The above outputs for Clinical outcomes will be based on the Safety Completers Population for the Interim Analysis and safety population for Final Analysis.

Data listings on clinical outcomes separately for hospital admission, ICU admission, oxygen support, death will be listed.

This document is confidential.

- AA (detected at >5% allelic frequency) changes in the SARS-CoV-2 spike protein in samples collected at Day 7, 14 and 28 (+/-2 days) compared to baseline following sotrovimab administration for samples with viral loads above the threshold of the sequencing assay

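### The SAP scores any post-baseline substitution as treatment-emergent without checking that both samples hold the same infecting virus

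*Protocol*

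**What the plan says.** **Target.** Protocol 8.3.2.1 is concerned with spike changes arising after treatment, found by setting each patient's follow-up sequence against that patient's own baseline sequence.

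**Scoring rule.** The opening of SAP section 10 defines treatment-emergent change, or change from baseline, as "any amino acid substitutions detected at post-baseline visits compared to baseline sequence". SAP 8.2 requires that baseline and post-baseline records both exist and sets thresholds: "Treatment emergence for consensus will include baseline records of allelic frequency $>5\%$ and post-baseline $>50\%$ as thresholds". For minority species the threshold is above 5% at both times. SAP 10.1 then tabulates patients for each substitution, by visit and overall.

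**Lineage.** For Secondary Objective 1, Protocol 8.7.1.2 says: "This analysis will be done on the earliest possible sample and reported only once per patient". SAP 10.2 likewise bases its summary on the "earliest possible VOC/VUI sample including baseline". It also promises a lineage listing, without saying which visits the listing covers. Under SAP section 5 the central laboratory sends a file with "viral variant calling VOC/VUI information based on the whole genome sequence", and the CRO merges it with the amino acid file.

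**Sample identity.** Protocol 8.1 states: "The patient's subject identification number must be present on each of the home test kits". Staff check this when the kits are handed out. Protocol 8.9 accepts that home collection cannot be verified, but discusses the consequence only for assay sensitivity.

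**The concern.** A baseline/post-baseline difference measures within-patient change only if both samples come from the same infection in the same person. Three situations break that condition: a new infection during the 28 days, a second virus that was not recorded at baseline, and a swab taken from somebody else. Under the stated rule each is scored as emergence wherever the two viruses differ in the scored region. The limitations in Protocol 8.9 mention none of the three.

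What is at stake is the meaning of the primary proportions and of the amino acid changes that Protocol 8.5 says go to the regulator patient by patient. A larger sample would not remove the error. The relevant rate is also the one among sequenced pairs, not among all patients. Protocol 8.5 expects many follow-up samples to hold too little virus to sequence. A fresh infection is plausibly easier to sequence than a clearing one, so discordance could be more common among sequenced late samples than in the whole cohort. That is reasoning; the documents give no data on it.

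**Working it through.** **1. The plan's own precision.** Protocol Table 2 uses the score interval with continuity correction. With n = 500, p = 0.09, q = 0.91 and z = 1.96:

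- Lower limit = [2np + z² − 1 − z√(z² − 2 − 1/n + 4p(nq + 1))] / [2(n + z²)] = (92.84 − 25.25)/1007.68 = 6.7%
- Upper limit = [2np + z² + 1 + z√(z² + 2 − 1/n + 4p(nq − 1))] / [2(n + z²)] = (94.84 + 25.50)/1007.68 = 11.9%

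Both match the protocol, so the precision figures are not in question.

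**2. Inputs for the bias.** The planning rates come from Protocol 8.5: epitope about 9% and 20%, and spike about 52% and 80%, at 15% and 5% allelic frequency respectively. No rate is given for the SAP's consensus threshold of above 50%. The epitope has 23 residues, described as more than 99.68% conserved (Protocol 6.1). Two quantities have to be assumed:

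- f, the share of analysed patients whose post-baseline sequence is an unrelated virus;
- s, the probability that the two viruses differ in the scored region.

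**3. Formula.** If true changes are still detected, only patients who would otherwise be negative can be mis-scored:

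observed = p + f·s·(1 − p)

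Example: 0.09 + 0.02 × 1 × 0.91 = 0.1082.

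| True rate p | s | f = 1% | f = 2% | f = 5% |
|---|---|---|---|---|
| Epitope 9% | 0 | 9.0% | 9.0% | 9.0% |
| Epitope 9% | 0.5 | 9.5% | 9.9% | 11.3% |
| Epitope 9% | 1 | 9.9% | 10.8% | 13.6% |
| Epitope 20% | 1 | 20.8% | 21.6% | 24.0% |
| Spike 52% | 1 | 52.5% | 53.0% | 54.4% |
| Spike 80% | 1 | 80.2% | 80.4% | 81.0% |

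**4. In patients.** At n = 500, f = 2% and s = 1:

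- Epitope 9%: 500 × 0.0182 = 9.1 extra positives, 9.1/54.1 = 17% of all positives.
- Spike 52%: 500 × 0.0096 = 4.8 extra, 1.8% of positives.
- Spike 80%: 500 × 0.004 = 2 extra, 0.5% of positives.

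With s = 1, the lower 95% limit rises above the true value at about f = 2.9% for epitope 9%, and at about 9.4% for spike 52%.

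**5. If the foreign sample replaces the patient's own.** Suppose it is that patient's only post-baseline sequence. A true change is then lost, and observed = (1 − f)p + f·s. For the epitope with p = 9%, f = 2% and s = 0, this is 0.98 × 0.09 = 8.8%, below the truth. The bias is upward only when s exceeds p.

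**6. Per-substitution rows.** One unrelated pair adds one patient to every row at which the two viruses differ. A row with k true patients shows k + 1, so a row with none shows a substitution that did not arise in any treated patient's virus.

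**The case against.** The strongest reply is that the documents give no frequency for these events, that the overall spike proportion barely moves, and that the study is descriptive and disclaims inference about the role of sotrovimab (Protocol 8.7.1 and 8.9). There are also partial safeguards. The baseline threshold of above 5% applies even to consensus emergence, so a co-infecting virus already above that level is in the baseline record. Kit identity is checked at dispensing. Treatment-emergent substitutions and lineages are listed, so a wholesale switch could be noticed. Laboratory procedures sit in a manual that was not available here.

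Much of this stands, and it rules out four stronger readings that a reader might infer:

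- *That once-per-patient lineage reporting causes the problem.* It governs only how Secondary Objective 1 is summarised. Changing it would leave both primary proportions as they are.
- *That both primary endpoints are necessarily inflated.* The epitope endpoint gains a false positive only if the viruses differ at one of 23 conserved residues. The documents give no epitope differences between lineages.
- *That the bias can only be upward.* Step 5 of the working shows the exception.
- *That any kit mix-up creates false emergence.* Exchanging one patient's own kits shifts the visit but introduces no foreign virus; only a swab from another person does.

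The safeguards still leave the gap open. A check at dispensing cannot show whose swab was returned. The baseline threshold does not cover a later infection. A listing does not remove a case from a proportion. The GISAID step is a feasibility exercise (SAP section 6) and asks whether a change has been reported elsewhere, not whether two samples are related.

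**Conclusion.** The gap is real: as written, SAP 8.2 and section 10 score a pair of unrelated viruses as treatment-emergent wherever they differ. The size is unknown because f and s are both assumed. At f = 2% the 9% epitope rate would read 9.0% to 10.8%, and at f = 5% it would read 9.0% to 13.6%, in each case provided true changes are still detected. The overall spike proportion is robust, moving by at most 1.0 percentage point at f = 2%. The rows for individual substitutions are the most exposed. The sample size and stated precision are unaffected. The change is worth making because it is cheap and shows both versions, not because a large bias has been demonstrated.

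**What to change.** In SAP 8.2 and 10.1, add a concordance check for each baseline/post-baseline pair, using lineage or whole-genome relatedness. Flag a pair when the post-baseline lineage is neither the same as the baseline lineage nor a descendant of it. List the flagged pairs, and report both primary proportions with and without them. Say how a patient with one flagged and one unflagged visit is counted.

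The variant calls or raw sequences described in SAP section 5 should suffice, but the sponsor should confirm that calls are delivered for every sequenced visit and not only the earliest.

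State the limits in the SAP and the report. A same-lineage reinfection or a same-lineage swab from another person may go undetected, so the version without flagged pairs is not proof of within-host emergence. Calls on partial genomes are uncertain, so a few genuine pairs may be removed, which is why both versions are needed. Add reinfection, co-infection and sample identity to the limitations.

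The cost is one derived flag, one listing and one extra row in the primary tables.
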